4.4 Dosage and labeling

SSKI. Subjects will be administered 130 mEq of a potassium iodide solution before administration of the tracer. The KI will be supplied by the Hospital pharmacy as per USP, either 16 drops of a 5% wt/vol Lugol's preparation or 5 drops of a super saturated potassium iodide solution.

[I-123] Radioactivity. The dose of 111 to 185 MBq (3 to 5 mCi) for each DaTscan [I-123] will be administered for each scan and will be given as per the package insert with regard to dose and route of administration. The amount of radioactivity in each syringe containing [I-123] DaTSCAN will be measured in a Capintec CRC Radioisotope Calibrator before and after injection.

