DaTSCAN is a currently approved radiopharmaceutical that enables measurement of both the serotonin and dopamine transporter in a single scan. DaTscan binds to both the serotonin transporter (SERT) and dopamine transporter (DAT) so that we can measure both neurotransmitter systems with a single scan. DaTscan requires preadministration of Lugol's solution which helps to block the thyroid gland from exposure to the I-123 isotope that is part of DaTscan. This is standard protocol for diagnostic studies of this type. DaTscan is injected intravenously and then SPECT imaging is performed approximately 3 hours post injection. The images can then be quantitatively analyzed to determine SERT and DAT binding by analyzing the midbrain and basal ganglia respectively. SERT and DAT activity has been widely evaluated in a number of disease states such as Parkinson's disease and depression. DaTscan is therefore an excellent tracer for its cost, availability, and ability to quantify changes in SERT and DAT binding in association with a meditation retreat.

Functional Brain Imaging Studies of Meditation

We are aware of a growing number of reports utilizing functional brain imaging techniques for studying subjects practicing meditation. In two studies, positron emission tomography (FDG-PET) was used to measure changes in glucose metabolism in subjects undergoing Yoga meditative relaxation (Herzog 1990-1991; Lou 1999). A third, functional magnetic resonance imaging was used to measure similar changes in subjects practicing a yoga relaxation technique (Lazar 2000). We have conducted a study of cerebral blood flow utilizing SPECT imaging (see below). One study utilized FDG PET to evaluate the Dopaminergic system during meditation. This latest study demonstrated significant increases in dopaminergic tone in the basal ganglia associated with meditation.

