4.2 Trial Design

Overall:

This study will initially utilize DaTSCAN and fMRI in healthy subjects within one month of entering a meditation retreat program. In addition, they will complete a variety of questionnaires and scales to assess their psychological status. They will then undergo the retreat and will return within one week of completing the retreat to repeat the scans and questionnaires. Thus, they will receive 2 DaTSCAN scans and 2 fMRI scans over the course of the study.

Time	Procedure
09:00 a.m.	Subject arrival. Review informed consent procedures.
09:30 a.m.	beta-HCG (if necessary)
09:45 a.m.	SSKI (Lugol's solution)
10:00 a.m.	Insert i.v. catheter
10:15 a.m.	Inject DaTSCAN
11:00 a.m.	Subject may take a break for 4 hours during which several
	qualitative scales will be performed
01:15 p.m.	Begin SPECT imaging
02:15 p.m.	SPECT scan completed
02:30 p.m.	Study completed

Approximate Timeline for DaTSCAN SPECT

Medical assessment procedures. A trained physician will take a detailed medical history on each subject and perform a standardized review. Structured physical, neurological, and psychological examinations will be performed. A set of clinical laboratory studies may be used to screen potential subjects with benign histories and normal physical examinations. A urine test for pregnancy will be performed in all women of childbearing potential. Female subjects with negative pregnancy tests will be enrolled.

Quantifying subjective phenomena. This protocol will add the administration of a number of neuropsychological tasks, psychological inventories, and spiritual scales at the time of imaging. These tests and questionnaires should take approximately two hours to complete, and many have already been widely used in both control and patient populations. These well established tests

were originally validated in large populations of people, and have since been used extensively in both clinical and research settings. Our lab has its own normative data base, which has been generated for people of all age ranges. The battery may include the following tests:

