b) DaTSCAN SPECT ACQUISITION, PROCESSING, AND ANALYSIS – Subjects will be asked to arrive at the Nuclear Medicine SPECT Center in the morning. A signed consent form will be documented after all questions have been answered. Women of child-bearing potential *must* have a negative pregnancy test within 48 hours *before* proceeding with the SPECT study. Subjects will be given 16 drops of concentrated Lugol's solution in order to block the thyroid. An intravenous catheter will be inserted and capped. Subjects will spend 20 minutes lying supine on an examination table before the radiopharmaceutical is administered to allow them to recover 'physiologically' from the stress of the catheter insertion. 111 to 185 MBq (3 to 5 mCi)¹²³I DaTSCAN will then be administered intravenously. After injection of the ¹²³I DaTSCAN, the subject will have the intravenous catheter removed. They will be able to take a break for lunch. Subjects will then return to the nuclear medicine imaging room 3 hours after ¹²³I DaTSCAN administration for a 60 minute brain scan. The reason for this delay is that kinetic modeling data performed on ¹²³I DaTSCAN has demonstrated that estimation of the binding potential can be made without arterial sampling at this time period (Acton 1998). The subject can be moved from the imaging table after the SPECT study is completed.

All SPECT images may be coregistered with the corresponding anatomic MRI and a previously described template (Resnick 1993), focusing on selected ROIs, will be fit on each

MRI and copied onto the DaTSCAN SPECT images. These ROIs will include the basal ganglia, amygdala and hippocampus, thalamus, brain stem, and cerebellum. To reduce the effects of volume averaging in the axial direction, ROIs will not be placed on the slices that contain the upper most and lower most portions of the structures they represent. This will tend to limit the small ROIs to the central aspect of structures they represent. The primary outcome measure will be the SERT and DAT binding ratios in which the ROI is compared to a reference region (cerebellum) at 4 to 5 hours post administration, when the distribution of ¹²³I DaTSCAN has approached a transient, near equilibrium-like state that reflects the k3/k4 ratio and is related to the binding potential. This allows for a quantitative assessment of SERT binding as described in the Preliminary Studies section.

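### Section 4.4 states the thyroid-blocking dose as 130 mEq of potassium iodide (about 21.6 g), which neither of the drop counts in the next sentence can deliver

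*Combined protocol and SAP*

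**What the plan says.** The dosing section, 4.4 Dosage and labeling, gives the amount as "Subjects will be administered 130 mEq of a potassium iodide solution before administration of the tracer". The sentence after it has the hospital pharmacy supply the agent to USP, as "either 16 drops of a 5% wt/vol Lugol's preparation or 5 drops of a super saturated potassium iodide solution".

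Elsewhere the agent appears without a chemical amount:

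- Section 4.2, in the SPECT acquisition text, repeats one of the two drop counts: "Subjects will be given 16 drops of concentrated Lugol's solution in order to block the thyroid". It gives neither mEq nor mg.
- The imaging-day timeline in Section 4.2 lists the agent by name only.
- Section 2.2 says "DaTscan requires preadministration of Lugol's solution which helps to block the thyroid gland", again with no amount.

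No section restates, corrects or explains the 130 mEq.

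**The concern.** Two adjacent sentences in the dosing section describe the same dose, and they cannot both be right. A milliequivalent of potassium iodide is 166 mg, so 130 of them come to tens of grams. A handful of drops holds tens to hundreds of milligrams.

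The 130 mEq is the only chemical amount the protocol gives for this agent. The participants are healthy volunteers, and the agent precedes the tracer at both of the two DaTSCAN sessions. A pharmacist, monitor or ethics board checking the drops against the stated dose could not reconcile them, and would find no mg figure to fall back on.

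**Working it through.** **Inputs from the documents** (Section 4.4): 130 mEq; 16 drops of Lugol's at 5% wt/vol; 5 drops of saturated potassium iodide.

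**Chemical constants:** potassium iodide is monovalent with molar mass 166.0 g/mol, so 1 mEq = 166.0 mg. The atomic mass of iodine is 126.9.

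**Assumptions, because the documents are silent:** 10 to 30 drops/mL; saturated solution at 1.0 to 1.4 g/mL; Lugol's 5% read either as 50 mg/mL potassium iodide, or as 5% iodine plus 10% potassium iodide.

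**Step 1. Convert the stated dose.** 130 × 166.0 mg = 21,580 mg, or about 21.6 g.

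**Step 2. Amount each drop would have to carry.** 21,580 / 16 = 1,349 mg per drop of Lugol's; 21,580 / 5 = 4,316 mg per drop of saturated solution.

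**Step 3. Amount the drops can carry.** Content = drops ÷ (drops per mL) × strength. Shortfall = 21,580 ÷ content.

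| Preparation | Strength (mg/mL) | Content at 10 / 20 / 30 drops/mL (mg) | Shortfall (fold) |
|---|---|---|---|
| Saturated, 5 drops | 1,000 | 500 / 250 / 167 | 43 / 86 / 129 |
| Saturated, 5 drops | 1,400 | 700 / 350 / 233 | 30.8 / 61.7 / 92.5 |
| Lugol's, 16 drops, 5% read as potassium iodide | 50 | 80 / 40 / 27 | 270 / 540 / 809 |
| Lugol's, 16 drops, 5% iodine + 10% potassium iodide: potassium iodide only | 100 | 160 / 80 / 53 | 135 / 270 / 405 |
| The same, with iodine converted to potassium iodide equivalent | 165.4 | 265 / 132 / 88 | 82 / 163 / 245 |

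The 165.4 in the last row is 50 × 166.0/126.9 + 100. That row is an equivalent, not potassium iodide actually present.

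The largest amount anywhere in the table is 700 mg, which is 700 / 166.0 = 4.2 mEq. The smallest shortfall is 21,580 / 700 = 30.8-fold.

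**Step 4. Check that the conclusion does not hang on drop size.** Solve for the drop volume needed to reach 21,580 mg:

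- Saturated at 1,400 mg/mL: 21,580 / 1,400 = 15.4 mL in 5 drops, about 3 mL per drop.
- Lugol's at 165.4 mg/mL: 130 mL in 16 drops, about 8 mL per drop.
- Lugol's at 50 mg/mL: 432 mL in 16 drops, 27 mL per drop.

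None of these is a drop.

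**Step 5. Try the obvious unit slip.** If mg was meant, 130 mg = 0.78 mEq, which is of the order that the drops deliver. At 20 drops/mL, Lugol's read as 5% iodine plus 10% potassium iodide gives 132 mg equivalent. Five drops of saturated solution, however, give 167 to 700 mg over the assumed range and never as little as 130 mg.

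**The case against.** The best defence is that the error does no work. The staff member giving the dose follows the drop count, which stands next to the mEq figure. The pharmacy supplies the agent to USP, and Section 4.2 repeats the 16 drops of Lugol's. Nothing else in the protocol is computed from 130 mEq. This stands, and it limits how much the error matters. It does not make the stated amount correct.

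A second objection is that the fold-differences rest on drop sizes and strengths that the documents do not give. That also stands for the numbers: about 31-fold is a floor only under the most generous assumptions (10 drops/mL and 1.4 g/mL), and should not be read as a bound taken from the protocol. It does not touch the contradiction, since even at that strength each drop would have to measure about 3 mL.

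A reader might go further and infer that volunteers would be given 21.6 g. The documents do not support this, because giving that amount would mean disregarding both drop counts. A reader might also infer that mg was certainly intended. The resemblance to 130 mg is suggestive, but no section states a mg amount, and over the assumed range the saturated-solution option does not equal it.

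**Conclusion.** The 130 mEq in Section 4.4 is wrong as written. It equals about 21.6 g. Under the assumed drop sizes and strengths, 5 drops of saturated solution fall about 31- to 129-fold short. Sixteen drops of Lugol's fall 270- to 809-fold short if 5% means potassium iodide, or 135- to 405-fold short on actual potassium iodide if it means 5% iodine plus 10% potassium iodide (82- to 245-fold if the iodine is counted as well). The contradiction holds for any realistic drop; the exact ratios depend on the assumptions.

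A unit error is the probable explanation, but the intended unit and amount are not established. The point is minor. It concerns a drug amount in the dosing text and has no bearing on endpoints, sample size or analysis.

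**What to change.** Delete the 130 mEq from Section 4.4, or replace it with an amount in mg, confirmed by the pharmacy, for each of the two permitted preparations. Do not simply change mEq to mg. State the strength of each preparation, check both drop counts against the confirmed amount, and keep the counts once they agree.

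The cost is one pharmacy check and a one-sentence edit. Design, sample size and analysis do not change.

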4.5 Duration of Participation

Subjects will undergo the SPECT and fMRI scan in one day and will be followed for the course of that day. Subjects will also be scanned following the meditation retreat program. Thus, subjects will undergo a second SPECT and fMRI scan and will be followed for the course of that day.

4.6 Discontinuation Criteria

Individual Subjects: Since I-123 DaTSCAN is a commercially approved diagnostic radiopharmaceutical, it is not anticipated that there should be any pharmacological response that would necessitate stopping an individual from participating in the scanning procedure. In the event that the subject cannot tolerate lying still in the scanner due either to pain or claustrophobia, then efforts will be made to allow for mild pain relief medications or sedation of the subject, as determined by their referring physician, and provided that they have a person who can transport them home after the scan, or the subject may withdraw from the study without prejudice. If the subject develops a systemic allergic reaction such as generalized hives, shortness of breath or hemodynamic compromise, the current scanning session will be terminated and the subject will no longer participate in the study. However, the subject will continue to be followed from a safety and clinical perspective at six months after the adverse event or every six months until the event resolves.

4.7 Accountability Procedures

The drug will be obtained from GE Healthcare and handled by the Nuclear Medicine department using the standard procedures for clinically approved radiopharmaceuticals.

4.8 Randomization Codes

Since this is a diagnostic study, subjects are not randomized.

4.9 Case Report Forms

All safety and scan procedural information, including radiopharmaceutical information and dose, adverse events, and subject reports will be included in the case report forms and adverse event forms as indicated. Subject source data including exam findings, medications, and prior radiographic and scintigraphic studies when deemed necessary by the principle investigator, to assess proper use of inclusion and exclusion criteria will also be included and to ensure all criteria are met (see below).

The DaTSCAN and fMRI scans and the qualitative and quantitative data will be kept as computer files and will not be a part of the case report forms.

5. Selection and Withdrawal of Subjects

5.1 Subject Inclusion Criteria

a. Subject selection

Subjects will be given informed consent at the Myrna Brind Center of Integrative Medicine or in the Department of Nuclear Medicine on the day of the study. After signing informed consent, all subjects will receive a physical, neurological, and psychiatric evaluation to ensure that none of the study subjects has a disorder that might affect cerebral metabolism, blood flow, or other brain functions (i.e. stroke, tumor, epilepsy, Axis I psychiatric disorders). Screening laboratory studies assessing electrolytes, complete blood cell count, liver function, thyroid function tests, pregnancy test if necessary, and urine toxicology screen may be obtained in order to confirm the subject meets inclusion criteria as determined by the PI.

Subjects will be excluded if: (1) they are taking medications that may alter cerebral blood flow as per the P.I., although supplements and medications to aid with mild dementia will be allowed if on a stable regimen, (2) they cannot lie still in the scanner due to physical or psychiatric reasons as per the P.I., or (3) they have physical, neurological or psychological disorders that might affect cerebral metabolism or blood flow as per the Principal Investigator. Female subjects of childbearing potential who are not pregnant or breastfeeding will be included in the study if they have received a negative pregnancy test (blood or urine) within 48 hours from the day of the study.

The subjects will meet the following criteria:

Inclusion criteria.

- 1. Able to give informed consent and willing to complete the study.
- 2. Willing to undergo the full imaging procedures.
- 3. Women of childbearing potential with a negative serum pregnancy test.

Exclusion criteria.

- 1. Any neurological or psychiatric disorders, including drug or alcohol abuse, that may interfere with cerebral blood flow as determined by the principle investigator.
- 2. Any medical conditions that may interfere with cerebral blood flow as determined by the principle investigator.
- 3. Currently taking medication that might affect cerebral blood flow (i.e. antidepressants, antipsychotics, anxiolytics, benzodiazepines, sedatives, antiseizure medications)
- 4. Subject is unable or unwilling to lie still in the scanner (i.e. due to claustrophobia or weight > 350 pounds)

- 5. Subject has metal in their body or other reason that they cannot undergo magnetic resonance imaging.
- 6. Previous brain surgery or intracranial abnormalities they may complicate interpretation of the brain scans (e.g., stroke, tumor, vascular abnormality).
- 7. Pregnancy.
- 8. Allergy to iodine or shellfish.
- 9. Concurrent participation in another research protocol that might affect the outcome of this study as determined by the principle investigator.

b. Sample Size

We anticipate recruiting up to 30 subjects for the study.

5.3 Subject Withdrawal Criteria

- 5.3.a. When and How to Withdraw Subjects
 - a. The subject cannot tolerate lying still in the scanner due either to pain or claustrophobia that cannot be corrected by pain medications or sedation of the subject.
 - b. The subject develops a systemic allergic reaction.
 - c. The subject experiences significant hemodynamic compromise that requires medication and hospitalization.
 - d. The subject is free to withdraw at any time they choose without affecting their continuing care for their illness.
 - e. If any of the above criteria are met, the subject will no longer undergo DaTSCAN scans. A discontinuation form will be completed and placed in the subject's binder.
 - f. If a subject is withdrawn, they will be requested to continue follow up only if they experienced an adverse event as per the protocol.

5.3.b. Type and Timing of Data Collection

1. All data will be collected at the time of the scanning procedure and at the time that it is determined that the subject is to be withdrawn from the study.

2. Any data from the scan will be removed from the data analysis due to possible confounding of the actual scan data related to the subject's inability to complete the scan.

3. Clinical data that can be used as part of the study can continue to be evaluated and the subject may continue with a clinical arm of the trial. However, the subject's data will not be included in any analysis of DaTSCAN or fMRI scan findings and their relationship to clinical variables.

5.3.c. Subject Replacement

Subjects that cannot or do not complete the study will be replaced in order to obtain enough data. If a subject experiences a serious adverse event directly related to the DaTSCAN or fMRI scan, then no further subjects will be recruited until the cause of the event is determined and it is ensured that no future such events will occur.

5.3.d. Follow up of Withdrawn Subjects

1. They will continue to have medical follow up as necessary.

6. Treatment of Subjects

6.1 Treatment to be Administered

DaTSCAN is not a therapeutic radiopharmaceutical. However, as a diagnostic agent, it will be administered intravenously in a single bolus.

6.2 Other Medications Permitted and Not Permitted

This is a study of healthy controls. Medications will be reviewed by the Principal Investigator prior to imaging. Subjects may not have taken Prozac for 6 weeks, SSRIs for two weeks. Vitamins, over the counter drugs and herbal supplements will also be evaluated.

6.3 Subject Compliance

Since the DaTSCAN SPECT and fMRI scans are given only in the hospital setting, all subjects will necessarily be compliant.

7. Assessment of Efficacy

7.1 Specification of Efficacy Parameters

This study will determine if there is a change in DaTSCAN related to meditation programs.

7.2 Methods and Timing for Evaluating Efficacy

We will evaluate changes in DaTSCAN and regional CBF related to the meditation programs before and after the program. The scans are performed in a single day.

8.1 Specification of Safety Parameters

Safety Assessment: DaTSCAN is a commercially approved tracer so this study is not designed to specifically evaluate safety. However, subjects will be asked if they experienced any unusual effects during the study and the debriefing period. Any adverse events will be recorded in the subject's data, either in the case report form or on the serious adverse events form.

Safety Evaluation: Adverse events will be recorded in the subject's data. Additional side effects and symptoms will be recorded in each subject's case report forms. This data will be pooled at the conclusion of the study in order to assess any additional safety concerns with the radiopharmaceutical or the imaging procedure. It should be noted that any study participant who experiences a serious adverse event directly related to the DaTSCAN will be excluded from further study using this radiopharmaceutical. For the purposes of this study, any adverse events or serious adverse events occurring within the duration of the study procedures that include the administration of DaTSCAN and the SPECT scan will be recorded and reported as indicated by regulation and IRB policy. However, events occurring after the SPECT scan dates and prior to the follow up scan dates will not be considered adverse events for the purposes of this study.

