2.3 Risks and Benefits

- **Potential Risks of Radiation Exposure:** The I-123 label on I-123 DaTSCAN is radioactive, which results in some exposure to ionizing radiation. The amount is acceptable for human research in subjects who will not benefit from the test.
- **Pharmacological Risks:** No pharmacological effects have been encountered in animal models or in human subjects for DaTSCAN.
- Special Risk Factors: There are no significant additional risks.
- **Risks of venous cannulation.** Venous cannulation is a routine clinical procedure that carries minimal risks when performed by trained personnel. It is possible that bruising could occur in some subjects. There is a theoretical risk of phlebitis or infection which is very remote.
- **Blood loss.** The maximum amount of blood that will be drawn from each subject will be less than 4 Tablespoons (< 1 fluid ounces). This is less than half the amount of blood that volunteers donate to the Red Cross (450 mls). Additional screening will only be performed if not already performed for clinical purposes.

Teratogenic Effects: Pregnancy Category C

Animal reproduction studies have not been conducted with I-123 DaTSCAN. It is not known whether DaTSCAN injection can cause fetal harm when administered to a pregnant woman or can affect reproduction capacity. Therefore, DaTSCAN injections should not be administered to a pregnant woman unless the potential benefit justifies the potential risk to the fetus.

Nursing Mothers

The effects of DaTSCAN injection on human breast milk are unknown.

We will not enroll a woman who is nursing or pregnant into the study.

MRI Risk: The fMRI scan does not involve any radiation exposure. Due to the strength of the magnetic field of the MRI, there is a risk of being injured if an unsecured metal object flies into the MRI scanner. In order to minimize this risk, you will be asked to remove all metal objects from your person. Also, all metal objects will be cleared from the area prior to the scan. This is

the standard practice when subjects undergo MRI exams. It is important when discussing the study that you inform the staff if they have any of the following:

- Surgically implanted electrical devices
- Pacemaker
- Surgically placed metallic clips (aneurysm clips)
- Ear implants
- Any history of metal fragments in the eye

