The Speilberger State Trait Anxiety Inventory (STAI) contains a total of 40 questions, half of which relate to the way subjects are feeling at the moment and half of which ask them to describe how they usually feel. The Profile of Moods Scale (POMS) will be administered. The Beck Depression Inventory (Beck 1972) is a standard 21 item questionnaire probing cognitive and somatic symptoms of depression. Additional scales may include: Short Form-12; Hood Mysticism Scale (Lifetime); Brief Multidimensional Measure of Religiousness/Spirituality; Gratitude Questionnaire; Daily Spiritual Experience Scale; ASPIRES (self-rated and observer-rated transcendence); Index of Core Spiritual Experiences (INSPIRIT); FACIT-Sp-12; Cloninger Self-Transcendence Scale, and Five Facet Mindfulness Questionnaire.

Women and minorities. While this is a limited study in terms of subject numbers, all efforts will be made to select volunteers that reflect the diverse demographics of the local urban community will be recruited for this project. It should be possible to enroll essentially equal numbers of men and women. All of our previous studies have suggested that it will be feasible to recruit a racially mixed population of subjects that includes African Americans and people whose families originated from the Pacific Rim.

Imaging Procedures.

a) OVERVIEW – All subjects will receive a DaTSCAN SPECT scan and an fMRI scan within 7 days of each other and within one month of beginning the meditation retreat program. fMRI scans will be performed within the same period of time, ideally on the DaTSCAN imaging day. Subjects repeat the neuroimaging battery and neuropsychological tests to evaluate for change after the retreat program. Subjects may engage in various activities or practices in between the scans in order.

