8.3 Procedures for Eliciting Reports and Reporting Adverse Events

Subjects will be evaluated during the injection period, immediately post injection, and prior to leaving on the day of imaging with a brief examination of the injection site and with a clinical evaluation to determine if the subject had any unusual experiences during the injection or scanning procedure. Subjects will be contacted by phone approximately one week after the scanning in order to assess for any further adverse events. For the purposes of this study, any adverse events or serious adverse events occurring on the day of administration of DaTSCAN and scan will be recorded and reported as indicated by regulation and IRB policy. After the imaging day , the subject will be considered to have completed the study and will not longer be followed.

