8.4 Type and Duration of Follow-up of Subjects After Adverse Events

Subjects will be followed six months after the injection if they experienced an adverse event directly related DaTSCAN. If there is no further problem, this will terminate the follow up. However, if the subject continues to have problems directly related to the DaTSCAN, then they will continue to be followed at six months intervals until the adverse event resolves or until the subject's death.

9. Statistics

9.1 Description of Statistical Methods Region of Interest Analysis.

The images of each of the scans will be reconstructed and resliced, using an oblique reformatting program, according to the anterior-posterior commissure line. The SPECT images will be co-registered with the anatomical MRI and comparable slices of the cerebral cortex will be examined. A previously validated template methodology consisting of regions of interest (ROI) corresponding to the major cortical and subcortical structures will be placed over the scans (Resnick 1993). For the purposes of this study, we will examine the regional CBF, serotonin transporter and dopamine transporter activity in only a selected number of ROIs which will be hypothesis driven. The ROIs to be examined based on the hypotheses described above and the preliminary findings will be the inferior frontal, superior frontal, dorsolateral prefrontal, orbitofrontal, dorsal medial cortex, inferior temporal, amygdala, hippocampus, superior parietal, inferior parietal, occipital, and sensorimotor areas, as well as the caudate, putamen, thalami, midbrain, hypothalamus, cerebellum, and cingulate gyrus regions. Each ROI will have its placement adjusted manually in order to achieve the best fit according to the atlas. The ROIs will then be copied directly onto each of the scans. This will be possible because the images will

already resliced into the same planes as described above. Counts will be obtained for each ROI and normalized to the mean whole brain counts. This will result in ratios of activity in each ROI will be compared across scans for each neuropsychological state. Other covariables such as age, and psychological measures, can also be included in the statistical analysis. The cerebral structures will be identified by their Talairach coordinates (Talairach 1988).

Statistical parametric mapping (SPM):

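### An event at an fMRI session held on a different day from the DaTSCAN SPECT falls outside the defined adverse-event window, although a serious fMRI-related event is a recruitment-hold trigger

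*Combined protocol and SAP*

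**What the plan says.** **Timing of the scans.** The imaging overview in section 4.2 states: "All subjects will receive a DaTSCAN SPECT scan and an fMRI scan within 7 days of each other". The same paragraph makes the DaTSCAN day the preferred day for the fMRI, not a required one. For the second round, 4.2 asks only that subjects return for the scans within one week of finishing the retreat. Sections 4.5 and 7.2 say that the scans are done in one day.

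**What counts as an adverse event.** Section 8.1 says that adverse events "occurring within the duration of the study procedures that include the administration of DaTSCAN and the SPECT scan will be recorded and reported", and adds that "events occurring after the SPECT scan dates and prior to the follow up scan dates will not be considered adverse events" for this study. Section 8.3 says that "any adverse events or serious adverse events occurring on the day of administration of DaTSCAN and scan will be recorded and reported", and that after the imaging day "the subject will be considered to have completed the study and will not longer be followed".

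**What depends on fMRI events.** Section 2.3 names the MRI hazard: "Due to the strength of the magnetic field of the MRI, there is a risk of being injured". Section 5.3.c makes it a trial-level trigger: "If a subject experiences a serious adverse event directly related to the DaTSCAN or fMRI scan, then no further subjects will be recruited". That hold lasts while the cause is being settled. Section 8.1 promises pooled safety data covering the imaging procedure as well as the tracer.

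**Follow-up of events.** Section 8.4 is limited to the tracer: "Subjects will be followed six months after the injection if they experienced an adverse event directly related DaTSCAN".

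**The concern.** The fMRI is a study procedure with a named risk and a role in the recruitment hold, yet the sentences that define the adverse-event window never mention it. When the fMRI shares the DaTSCAN day, this makes no difference to recording. When it does not, an event at the fMRI visit has no window to fall into, and in one situation the plan states outright that it is not an adverse event.

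Two things are at stake. The hold in 5.3.c relies on fMRI-related serious events being recognised, while the section that defines study adverse events can leave them out. The pooled safety summary could also be read as covering all study imaging when it covers only DaTSCAN days. The issue is a procedure without a collection window, not a late effect of the tracer.

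**Working it through.** The plan gives no figure to reproduce, so the check sets the rules side by side and then sizes the exposure.

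**Step 1. Is a separate-day fMRI allowed?** Under 4.2, yes: up to 7 days' separation at baseline, and no same-day requirement within the one-week return period at follow-up. The approximate DaTSCAN-day timetable in 4.2 runs from 09:00 to 14:30 and has no fMRI slot. Under 4.5 and 7.2, no. The documents conflict.

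**Step 2. Where does an event at each possible fMRI visit fall?**

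| fMRI visit | 8.1 | 8.3 |
|---|---|---|
| Same day as SPECT | Within the SPECT date | Within the recorded day |
| Baseline, after the first SPECT day | Inside the interval declared not to be adverse-event time | Outside the recorded day |
| Baseline, before the first SPECT day | Not in the excluded interval, and not named in the window | Outside the recorded day |
| Follow-up, after the second SPECT day | Not named in the window | Outside the recorded day, and after follow-up has ended |
| Follow-up, before the second SPECT day | Unclear: depends on whether the fMRI date counts as a follow-up scan date | Outside the recorded day |

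The second row is the clearest, because an explicit rule removes the event. The fourth is nearly as clear, because 8.3 has already declared the subject complete. The third rests on 8.3 alone.

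**Step 3. Which rules need these events?** Section 5.3.c names the DaTSCAN and the fMRI scan. The window sentences in 8.1 and 8.3 name DaTSCAN administration and its scan. Section 8.4 names only DaTSCAN. The trigger is wider than the window and the follow-up that should support it. The 8.4 mismatch remains even if every fMRI is on the DaTSCAN day.

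**Step 4. Exposure.** Inputs: 2 fMRI scans per subject (4.2); 25 subjects (9.2 and 9.4), with recruitment of up to 30 anticipated (5.1.b).

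- Sessions = scans per subject × subjects
- 2 × 25 = 50
- 2 × 30 = 60

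The documents do not give the share held on another day. The affected number is 0 if 4.5 and 7.2 are followed, and at most 50 or 60 if no fMRI shares a DaTSCAN day. These are counts of sessions, not expected events.

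**The case against.** The strongest reply is that the gap may never open. Sections 4.5 and 7.2 both describe one-day scanning, and if sites work that way no session is affected. This stands as a limit on size. It does not remove the point, because 4.2 contains the detailed imaging procedure and permits otherwise, and whether an event counts should not depend on which section staff follow.

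A reader might infer that a separate-day fMRI event would never be recorded. The documents do not support that. Section 8.1 opens with a general undertaking to record adverse events and to ask subjects about unusual effects, 4.9 puts adverse events in the case report forms without a tracer limit, and 8.3 plans a telephone call about a week after scanning. Any of these could bring an event to light. The later sentences in 8.1 and 8.3 nevertheless narrow what counts for this study. The 8.1 window could be read as non-exclusive, but the exclusion that follows it and the day limit in 8.3 favour the narrow reading.

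A reader might also infer that the recruitment hold would fail. Section 5.3.c turns on a subject experiencing the event, not on its being recorded under 8.1 or 8.3. Staff present at the fMRI could see an acute injury, and 9.4 separately provides for termination on serious adverse events without limiting them to DaTSCAN. What remains is that the plan gives no defined route from such an event to a study adverse event.

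Sections 5.3.a.f and 5.3.d offer some follow-up not tied to DaTSCAN, but only for withdrawn subjects. Metal screening and exclusion criterion 5 lower the MRI risk without changing the rules on recording.

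**Conclusion.** The point holds as a conditional inconsistency. If an fMRI is on a different day from the SPECT, as 4.2 allows, an event there is outside the defined adverse-event window and would not count as a study adverse event, although 5.3.c and the pooled safety summary in 8.1 call for it. The size is 0 to 50 sessions at 25 subjects, or 0 to 60 at 30, with the actual share unknown.

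The conclusion assumes that the narrowing sentences in 8.1 and 8.3 govern over the general one, and that the scan in 8.3 means the SPECT.

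Three wider readings go too far. The 8.1 exclusion does not reach a baseline fMRI done before the first SPECT; only the 8.3 day limit does. The 7-day allowance is explicit only for baseline; at follow-up the latitude comes from the one-week return period. And the gap gives no reason to widen 8.4 to iodide or cannulation, which take place on the DaTSCAN day and so within the window.

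**What to change.** 1. Reconcile 4.2 with 4.5 and 7.2 on whether SPECT and fMRI must share a day, at baseline and at follow-up.
2. In 8.1 and 8.3, define the adverse-event window to include every fMRI session day as well as every DaTSCAN/SPECT day, and reword the 8.1 exclusion so that it cannot cover an fMRI session.
3. In 8.3, end participation only after the later of the second SPECT and the second fMRI.
4. Reconcile 8.4, which covers only DaTSCAN-related events, with 5.3.c, which names both DaTSCAN and fMRI.

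The cost is protocol wording, one adverse-event question at each separate-day fMRI visit, where staff already see the subject, and a few more minor events on record. The sample size and the imaging analyses are unaffected.
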